	Mode of administration and dosage regimen	
Imupret® oral drops
 
Dosage for acute symptoms:
 
Children from 6 to 12 years: 15 drops 5-6 times daily
 
Adults and adolescents from the age of 12 years: 25 drops 5-6 times daily
 
Dosage after acute symptoms have subsided:
 
Children from 6 to 12 years: 15 drops 3 times daily
 
Adults and adolescents from the age of 12 years: 25 drops 3 times daily

Duration of treatment	
Disease will be evaluated 36-48 hours prior to active treatment.
 
Active Imupret® treatment group: 10 treatment days
 
Reference treatment group: 10 days
 
Afterwards, there will be a follow up observation phase of 1 months
	

SCHEDULE OF ASSESSMENTS

V1		V2		V3 (Telephone call)					V4	V5
day 1	day 2	day 3	day 4	day 5	day 6	day 7	day 8	day 9	day 10	day 28

Study group 1

Imupret (dosage acute phase)
Reference treatment

Study group 2

Reference treatment

V1	day 1	Screening, randomization, prescription of treatment
V2	day 3	Status evaluation, possible prescription of antibiotics
V3	day 5 ±1	Evaluation of treatment efficacy, telephone call
V4	day 10 ±1	Evaluation of treatment efficacy, end of reference treatment
V5	day 28	Telephone call

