It should be noted that unjustified antibiotic therapy of acute tonsillitis is only based on the symptom "sore throat" or "exudate (plaque) tonsils" and plays a significant role in the formation of antibiotic resistance. Antibiotic therapy does not affect pain. In order to avoid the

irrational use of antibiotics, one should distinguish the desire of the patient or his parents to get rid of the pain, from the rational assessment of the doctor for all pros and cons about an antibacterial therapy.

To prevent unjustified prescription of antibiotics, a therapeutic concept of delayed administration is proposed. A patient with acute tonsillitis is prescribed treatment with antibacterial agents in a delayed manner (a prescription is written out, the dose and the frequency of administration is calculated). In the absence of positive effect within 36-48 hours from the beginning of treatment with Imupret the antibacterial therapy with antibiotics is started. The advantage of deferred antibiotic prescription is, that a higher number of patients and doctors, awaiting antibiotic therapy, may be more agreeable with this way of treatment than with a complete rejection of the antibiotics prescription. This is why delayed use of antibiotics is an important treatment strategy to reduce the number of unreasonable prescription of antibacterial agents.

Considering this fact, it becomes necessary to use drugs with a complex effect on the main processes of pathogenesis and have an evidence-based efficacy base for acute tonsillitis. At the present moment, there is an insignificant evidence base for the application of the phytonoering drug Imupret in acute tonsillitis. The spectrum of its pharmacological properties includes antiviral, antibacterial, antiinflammatory and immunomodulating effects. The combination of these properties makes it possible to influence practically all parts of acute tonsillitis. Additionally a good safety profile allows to consider Imupret as an adequate basic therapy for the treatment of acute tonsillitis, especially in the therapeutic concept of of delayed prescription of antibiotics. The already existing studies were not conducted under GCP conditions. Confirmation of the high effectiveness of Imupret in the treatment of acute tonsillitis would serve as a rationale for optimizing the treatment regimen of this nosology and recommendations for the inclusion of the drug in national guidelines.

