6.3 Description and rationale for conducting the trial

At present, there is minor evidence of using the phytoengineering-based drug product Imupret® in acute tonsillitis, pharyngitis and tonsillopharyngitis. The spectrum of its pharmacological properties includes antiviral, anti-inflammatory, and immunomodulatory action. The aggregate of these properties allows affecting almost all pathogenetic process links underlying the nosology in question, and favourable safety profile allows viewing Imupret as a basic therapeutic agent in treatment of non-bacterial forms of acute tonsillitis, pharyngitis, and tonsillopharyngitis. Our previous work showed that the use of Imupret in patients with non-bacterial tonsillitis accelerates regression of symptoms of tonsillitis and reduces the need for antibiotics. At the same time, there is a lack of studies, valid from the viewpoint of compliance with GCP standards have been conducted. Confirmation of high efficacy of Imupret in treatment of the above nosology group would be served as a justification for optimization of this nosology treatment scheme of delayed antibiotic prescription and recommendations for inclusion of this drug product into the national guidelines.

In the context of this clinical trial the two questions that are to be answered are:

1. Does Imupret®, taken during the diseases acute period help reduce the frequency of antibiotic use in children aged 6-12 ?
2. Does Imupret®, taken during the diseases acute period helps to accelerate the regression of symptoms in children aged 6-12?
3. Is the use of antibiotic delay technology safe for children aged 6-12 years?

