7 TRIAL OBJECTIVES

The aims of this clinical trial are:

To investigate the influence of Imupret prescriptions in the therapeutic concept of delayed prescription of antibiotics to:

- To compare the need for antibiotics in patients, received Imupret in addition to conventional therapy and in patients of the control group (received conventional therapy only)
- To evaluate the effect of the study drug in complex with conventional therapy versus conventional therapy only on regression of the tonsillitis symptoms
- To evaluate the effect of the study drug in complex with conventional therapy versus conventional therapy only on duration of antipyretic (paracetamol as antipyretic) administration.

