8.3.3 Reference treatment

All patients of the trial will undergo the reference treatment described below. However, only one of the two study groups (study group 1) will receive and add-on treatment with either Imupret® oral solution (see 0 and 8.3.2).

Reference treatment comprises instructions for patient's behavior as well as possible medical treatment when needed:

- Sparing diet with fractional feeding (5-6 times a day) in only small portions explicitly excluding coarse, spicy, or heavily digestible food
- At the discretion of the investigator, elimination of all factors irritating pharyngeal mucosa (e.g. thermal, chemical influence etc.)

At the discretion of the investigator, Paracetamol as single doses up to 500 mg – not more than 3-4 times daily

- At the discretion of the investigator, topical treatment like benzydamine, lidocaine (in case of severe sore throat)
- At the discretion of the investigator, antibiotic treatment in case it is indicated with e.g. amoxicillin clavulanate, cephalosporins (in case of prescription of antibiotics patients will be evaluated separately)

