8.5 Time schedule and visits

Four scheduled visits will be performed during the first phase of the study:

First study phase

- 1 visit (1st day): screening, randomization and treatment; evaluation by Mc Isaac Score scale; LTM Scale (Local Tonsillitis Manifestation Scale): (5 symptoms: Sore throat at swallowing (0 – absent, 1 – mild, 2 – moderate, 3 – severe / pronounced); Sore throat at rest; Throat irritation at rest; Palatine tonsils hyperemia; Palatine tonsils edema); Patients self-assessment (VAS; 0-10)

- 2 visit (3rd±1 day): intermediate evaluation of the effectiveness of treatment - clarification of the patient's condition, the need to prescribe an antibiotic; evaluation by LTM Scale, patients self-assessment (VAS; 0-10)
- 3 visit: intermediate evaluation of the effectiveness of treatment (day 5-day ±1) via telephone (or visit if necessary); patients self-assessment (VAS; 0-10)
- 4 visit: final (10th day ±1 day). Evaluation by LTM Scale (0-15), patients self-assessment (VAS; 0-10)
- 5 Follow up; day 28: evaluation of the long-term effects of treatment
- - An unscheduled visit can be made if the patient's condition worsens (according to the patient and / or the researcher, including if the symptoms of the disease persist or worsen, including but not limited to an increase in the temperature in the armpit above 38.0 ° C at the 3rd and / or subsequent days of treatment).
- The total duration of the treatment: 10 days
- The total duration of the study for one patient is not longer than 38 days.

Any unscheduled visit may be carried out in case of worsening of the patient's condition (at patient's and/or investigator's opinion), including persistence or aggravation of the disease symptoms.

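### The synopsis places the 36-48 hour evaluation before treatment instead of after it, and the ±1 day window lets the scheduled antibiotic decision fall at about 24 hours

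*Protocol*

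**What the plan says.** The duration-of-treatment entry in the protocol synopsis reads "Disease will be evaluated 36-48 hours prior to active treatment". The synopsis uses the word active for the Imupret add-on: the next line of the same entry gives the length of the active Imupret group's treatment.

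The schedule under the synopsis lists V1, day 1, as "Screening, randomization, prescription of treatment" and V2, day 3, as "Status evaluation, possible prescription of antibiotics". It gives ±1 day for V3 and V4 but none for V2. Section 8.5 also starts treatment at the first visit, and section 10.1 has the study drug handed over at the end of that visit.

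Section 6.1 describes the delayed-prescription concept. Antibiotics are started "In the absence of positive effect within 36-48 hours from the beginning of treatment with Imupret".

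Section 8.5 gives V2 a window: "2 visit (3rd±1 day): intermediate evaluation of the effectiveness of treatment". It adds that the need for an antibiotic is judged then. Section 10.2 names day 3 but attaches the plus or minus one day to Visit 1; read beside 8.5, it means day 3±1. It leaves the antibiotic decision to the investigator and sets no hour limit.

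**The concern.** Two things do not fit together. The synopsis puts an evaluation before treatment that section 6.1 and the visit schedule put after it. And the window in 8.5 is wider than the interval in 6.1, so a V2 that complies with the protocol can take place before the delay has run.

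The delay is part of what the trial studies. Section 7 sets the aim as "To investigate the influence of Imupret prescriptions in the therapeutic concept of delayed prescription of antibiotics to" the outcomes it then lists, and the third question in section 6.3 is "Is the use of antibiotic delay technology safe for children aged 6-12 years". The V2 decision also feeds efficacy. Need for antibacterial therapy is a main criterion in section 12.2.2 and in the SAP, and the synopsis makes absence of an indication for antibiotics part of effective treatment. An antibiotic prescribed at a routine day-2 visit would count as need although the child had not completed the waiting period that defines the strategy.

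**Working it through.** **Order of events.** The two statements about the 36-48 hours, set beside the schedule:

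| Place | Position of the 36-48 hours |
|---|---|
| Synopsis, duration of treatment | before active treatment |
| Section 6.1 | after the beginning of treatment |
| Synopsis schedule, 8.5, 10.1 | screening, randomization and treatment all at V1, day 1; no earlier visit |

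Only the 6.1 reading is compatible with the schedule. Active cannot readily mean the antibiotic, since the synopsis uses it for Imupret.

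**Timing of V2.** Inputs: V1 on day 1 (synopsis, 8.5); V2 on day 3 (synopsis) or day 3±1 (8.5); delay 36-48 hours (6.1). With V1 as time zero, nominal time on study day d is 24 × (d − 1) hours.

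- Day 3: 24 × 2 = 48 hours. The nominal visit agrees with 6.1, at its upper limit.
- Day 2: 24 × 1 = 24 hours, which is 36 − 24 = 12 hours before the lower limit.
- Day 4: 24 × 3 = 72 hours, which is 72 − 48 = 24 hours past the upper limit.

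**Allowing for clock times.** V1 and V2 need not take place at the same hour. If the clinic day is w hours long, elapsed time lies in 24 × (d − 1) ± w. The documents do not give w, so a range is shown as an assumption:

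| w | Day 2 | Day 3 | Day 4 |
|---|---|---|---|
| 8 h | 16-32 h | 40-56 h | 64-80 h |
| 10 h | 14-34 h | 38-58 h | 62-82 h |
| 12 h | 12-36 h | 36-60 h | 60-84 h |

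For a clinic day shorter than 12 hours, every day-2 visit is earlier than 36 hours; at 12 hours the latest possible day-2 visit just reaches it. For a clinic day of up to 12 hours, no day-3 visit is earlier than 36 hours. Day-3 visits can run past 48 hours, so 48 hours works as a target and not as a strict limit.

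Time is counted from V1 because the documents do not give the time of the first dose. A first dose taken later than V1 would shorten the interval further.

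**The case against.** The best reply is that nothing goes wrong in practice. A reader might infer from the synopsis sentence that an untreated run-in of 36-48 hours is planned. The documents do not support that: no visit precedes V1, so no site could act on the sentence. It is a slip of wording, and the schedule shows the intended order. This stands.

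A reader might also infer that a day-4 V2 leaves a child without antibiotics for about 72 hours. That too goes too far. Section 8.5 allows an unscheduled visit if symptoms persist or worsen, and names as an example a temperature above 38.0 °C from the third day of treatment. Section 8.3.3 allows, "At the discretion of the investigator, antibiotic treatment in case it is indicated", without tying it to V2. The unscheduled visit is optional, but it covers most of the late side.

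Nor is it right that the visit sections leave the delay undefined: day 3 with a tolerance is a stated nominal time. What they lack is an hour limit. Section 6.1 is a background section, so its 36-48 hours need not be a hard rule. And although 6.1 speaks of treatment with Imupret only, the V2 decision and the antibiotic provision in 8.3.3 apply to all patients.

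Finally, nothing obliges the investigator to prescribe at a day-2 visit. That is true, but the protocol makes V2 the point at which the decision is taken and does not ask for it to be put off when V2 is early. The early side is the part that these replies leave open.

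**Conclusion.** The concern holds as a minor point. The synopsis sentence is wrong against section 6.1 and against the protocol's own schedule. The ±1 day at V2 lets the scheduled antibiotic decision fall on day 2, nominally 24 hours after V1, or 14-34 hours with an assumed clinic day of 10 hours. That is before the 36-48 hours that 6.1 gives as the delay.

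Because the trial is open-label, a reader might infer that the loose window biases the comparison of antibiotic need. The documents do not show this: the same window applies to both arms, and nothing indicates that visits would be timed differently. How many antibiotic decisions would change cannot be estimated from the documents, and no sample-size, power or error-rate figure depends on the point.

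The conclusion rests on counting from V1 as the start of treatment and on clinic days shorter than 12 hours.

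**What to change.** In the synopsis, replace the sentence with: *Disease status and need for antibiotics will be evaluated at V2, 36-48 hours (nominally day 3) after the start of study treatment, in both groups.*

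In the synopsis schedule, 8.5 and 10.2, define V2 in the same words: *day 3 (+1 day), not before 36 hours after the start of study treatment.* Add that this governs the scheduled visit only, and that earlier unscheduled visits and antibiotics remain allowed if symptoms persist or worsen. Because ordinary clock times can carry a day-3 visit past 48 hours, a visit inside the day window should not be a deviation for that reason alone.

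Optionally, add to the SAP a descriptive table, by arm, of time from V1 to V2 and from V1 to antibiotic start, so that the delay actually applied can be seen.

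The cost is a change of wording in a few places and, if wanted, one table. V2 booking becomes slightly tighter, and a few more visits may be recorded as outside the window. The case report form is not among the documents, so whether visit and first-dose times are already captured is unknown; if not, they would have to be added.

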6 INTRODUCTION

6.1 Medical background

The problem of acute inflammatory diseases of the tonsils is one of the most urgent in modern clinical medicine. The prevalence of pathology ranges from 2 to 15% of the total population. Morbidity is especially common among children: 50% of patients aged 5 to 15 years, often in early school age. The incidence among the age group 18 years and older is 11.36 cases per 1000 population per year, among children aged 0-17 years - 62.61. Such patients constitute a significant proportion of outpatients both among otorhinolaryngologists and pediatricians, and the diagnosis of inflammation of the lympho-pharyngeal apparatus is established in 19-20% of the cases among the 20 most commonly diagnosed diseases (in accordance to Medical Data Management).

Acute tonsillitis (ICD J03.0-J03.9) refers to viral or bacterial tonsillitis. Acute tonsillitis in most cases is due to viral infections. The most frequent pathogens are adenovirus, Epstein-Barr virus and enteroviruses, including Coxsackie viruses. Bacterial acute tonsillitis occurs in immunocompetent children in 20-30% of cases, adults - in 5-15%, and the most frequent cause of it is β -hemolytic streptococcus group A (GABS). Acute relapsing / recurrent tonsillitis (ICD J35.0) refers to repeated acute tonsillitis and is not a sign of bacterial tonsillitis.

Acute tonsillitis is defined as the sudden appearance of the following specific symptoms: sore throat, hyperemia, edema of the tonsils, increase in swollen lymph nodes (regional lymphadenopathy) and nonspecific additional symptoms like fever, weakness and joint pain. It has to be noticed, that there are no pathognomonic symptoms of bacterial tonsillitis. To assess the patient's condition and to determine the indications for antibacterial therapy, the McIsaac scale is a commonly used tool for decision. This scale is used to classify patients according to their symptoms and to determine the patients for whom antibiotic therapy is not indicated.

McIsaac scale (sum of scores)	The probability of the identification of β -hemolytic streptococcus in a smear from pharynx
-1 or 0	1%
1	10%
2	~17%
3	~35%
4 or 5	~50%

Thus, in most cases of acute tonsillitis (even if there are 4-5 points according to the scale), it has to be taken into account that there is a low probability of the presence of GABS. Therefore, there are no unconditional indications for the prescription of antibiotics.

It should be noted that unjustified antibiotic therapy of acute tonsillitis is only based on the symptom "sore throat" or "exudate (plaque) tonsils" and plays a significant role in the formation of antibiotic resistance. Antibiotic therapy does not affect pain. In order to avoid the

irrational use of antibiotics, one should distinguish the desire of the patient or his parents to get rid of the pain, from the rational assessment of the doctor for all pros and cons about an antibacterial therapy.

To prevent unjustified prescription of antibiotics, a therapeutic concept of delayed administration is proposed. A patient with acute tonsillitis is prescribed treatment with antibacterial agents in a delayed manner (a prescription is written out, the dose and the frequency of administration is calculated). In the absence of positive effect within 36-48 hours from the beginning of treatment with Imupret the antibacterial therapy with antibiotics is started. The advantage of deferred antibiotic prescription is, that a higher number of patients and doctors, awaiting antibiotic therapy, may be more agreeable with this way of treatment than with a complete rejection of the antibiotics prescription. This is why delayed use of antibiotics is an important treatment strategy to reduce the number of unreasonable prescription of antibacterial agents.

Considering this fact, it becomes necessary to use drugs with a complex effect on the main processes of pathogenesis and have an evidence-based efficacy base for acute tonsillitis. At the present moment, there is an insignificant evidence base for the application of the phytonoering drug Imupret in acute tonsillitis. The spectrum of its pharmacological properties includes antiviral, antibacterial, antiinflammatory and immunomodulating effects. The combination of these properties makes it possible to influence practically all parts of acute tonsillitis. Additionally a good safety profile allows to consider Imupret as an adequate basic therapy for the treatment of acute tonsillitis, especially in the therapeutic concept of of delayed prescription of antibiotics. The already existing studies were not conducted under GCP conditions. Confirmation of the high effectiveness of Imupret in the treatment of acute tonsillitis would serve as a rationale for optimizing the treatment regimen of this nosology and recommendations for the inclusion of the drug in national guidelines.

6.2 Drug profile

6.2.1 Pharmacology / Safety profile

6.2.1.1 Pharmacology

Herbal products containing individual drugs, similar to this herbal combination product, were developed several decades ago on the basis of traditional medical use. They have gained wide recognition and clinical application.

Pharmacodynamic *in vitro* and *in vivo* studies have demonstrated anti-inflammatory, antiviral and antibacterial, immune-modulatory properties of components of Imupret (please refer to 2.6.2 and 2.4) [Kommission E, 1984-1989 (1, 2, 3), 1990 (5, 6, 7), 1992 (8)].

The pharmacodynamic effects might be based on the more or less plant specific ingredients like flavonoids, polysaccharides, terpenoids, sesquiterpens etc. Pharmacokinetic data are not available to sufficiently show their systemic availability in humans. Effects of the single plants or of the extract from all plants contained in Imupret cannot clearly be linked to single plant specific ingredients. However, the effects of the complex extract have been investigated in in-vitro or in-vivo animal experiments. The results indicate that it displays the anti-inflammatory, antibacterial, antiviral, or immune-modulatory effects. This can also be measured after systemic application including oral and intraperitoneal administration. This indicates that the basic characteristics of the single herbal drugs known from administration according to the monographs are also displayed after systemic administration in the dosage and composition of Imupret (module 2.4).

It is generally accepted that the combination of drugs in a multi-component mixture may lead to increased or maintained efficacy while decreasing the dosage of the individual components to avoid toxicity. The mathematical basis of this concept was already set up in 1963 by Webb in a simplified model, the so-called 'fractional product method' [Webb, 1963 (9)].

6.2.1.2 Safety profile

Imupret and its herbal constituents *Althaeae radix*, *Millefolii herba*, *Taraxaci herba*, *Equiseti herba*, *Juglandis folium*, *Matricariae flos*, and *Quercus cortex* have a long history of traditional use. Furthermore, Imupret (formerly Tonsilgon) has been prescribed by doctors over several decades. From these applications a very good safety profile is apparent.

The data from all clinical surveys provide just one category of ADRs that came up: gastrointestinal complaints (0.17 %) that eventually stopped the patients from further taking Imupret.

As been described in 2.5.4, all surveys were performed in private practices of general practitioners or ENT doctors. Patients of all age groups have been included. The medical conditions investigated covered recurrent infections of the upper airways, including tonsillitis, catarrhal rhinosinusitis and tracheobronchitis.

In total, the intake of Imupret coated tablets or oral drops was monitored for 2483 patients. Both solid and liquid application forms have been used, numbers of applications of each formulation in the 2 older surveys of Maier and Maier 1974 [9] and Sprenger 1975 [10] are unknown. The large majority of patients were treated either for 2 weeks ([Berger T. 2008 (11), Vavilova V. et al. 2016 (12)]) or 3 months.

Adverse events:

Of 2 adverse events with Imupret oral drops reported in 1 of 3 surveys, both were related to the gastro-intestinal system: vomiting and stomach ache. Both were transitory; dose-withdrawal was the consequence in both cases. No adverse event was reported with the coated tablets in this surveillance.

Post-marketing experience:

Although more than 653 million DDDs of Imupret®/Tonsilgon® oral drops and coated tablets were marketed from 1973 until now, only 7 spontaneous cases of serious adverse drug reactions (sADR) in association with Imupret®/Tonsilgon® oral drops or coated tablets have been reported worldwide. Hereof only two cases of sADR were assessed as possibly related to the intake of Imupret®/Tonsilgon® by the MAH, one case was assessed as unlikely due to evident other reason and four cases were assessed as unassessable because of insufficient and / or contradictory information.

